8.7.2 Clinical and Subjective Opiate Withdrawal Scales

The COWS consists of 11 items to provide a description of the symptoms of withdrawal that can be directly observed by a physician interviewer: increased resting pulse rate, gastrointestinal upset, sweating, tremor, restlessness, yawning, pupil size, anxiety or irritability, arthralgias, piloerection of skin, and runny nose or tearing.

The total score of the COWS is the sum of the responses to the 11 items, which can range from 0 to 48, with higher scores indicating greater withdrawal severity. If there are missing items when the total score is calculated, the total score will be set to missing. Total score between 5 and 12 inclusive indicates mild withdrawal; between 13 and 24 inclusive indicates moderate withdrawal; between 25 and 36 inclusive indicates moderately severe withdrawal; and total score greater than 36 indicates severe withdrawal.

The SOWS is a self-rating scale which has been shown to be a reliable and valid measure of the opiate withdrawal syndrome. It contains 16 symptoms whose intensity the subject rates on a 5-point scale of 0 = not at all, 1 = a little, 2 = moderately, 3 = quite a bit, 4 = extremely. The total

score is a sum of item ratings, and ranges from 0 to 64. If there are missing items when the total score is calculated, the total score will be set to missing.

The total score for COWS and SOWS will be calculated at all scheduled assessment time points.

The COWS and SOWS total scores will be summarized descriptively. The total score of COWS will be summarized categorically by dose level.

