Following 51 weeks of NKTR-181 treatment, subjects will begin a 1-week taper from study drug. The NKTR-181 dose will be decreased over the 1-week period until all subjects are receiving 100-mg BID for at least 2 days. Subjects will return to the site for their End of Treatment visit (Visit 22/EOT). Following completion of Visit 22/EOT **or** completion of an ET Visit at any time after receiving study drug, subjects will proceed to the Safety Follow-Up Period.

The COWS and SOWS will be administered according to the Schedule of Assessments (Section 1.2) to monitor for opioid withdrawal. Subjects experiencing opioid withdrawal will be treated appropriately according to the Investigator's clinical practice.

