6.3 Safety Follow-Up Period (Visits 23-24)

To capture evidence of withdrawal following discontinuation of study drug, all subjects (including ET subjects) will record SOWS measurements and be administered COWS assessments as described in the Schedule of Assessments (Section 1.2).

During the Safety Follow-Up Period, clinical laboratory samples will be collected only if a prior laboratory result was considered abnormal and clinically significant.

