6.6.1 Prohibited and Restricted Medications

Subjects must not take any medication for chronic pain during the study (through the end of the Treatment Period) that was not provided by the sponsor (including rescue medication) and should be reminded of such at each study visit. Use of moderate to strong cytochrome P450 3A4 (CYP3A4) inhibitors and inducers is prohibited throughout the study.

Subjects who have been taking opioid-containing medications prior to study start (no less than 10 mg MSE/day and no more than 60 mg MSE/day) will be eligible to participate. However, the opioid must be tapered to no more than 30 mg MSE/day for at least 3 days prior to Visit 3, then completely discontinued prior to starting NKTR-181. Concomitant use of opioids with NKTR-181 is prohibited. Use of these medications will be documented on the concomitant medication eCRFs and will include start and stop date, dose and route of administration, dosing frequency, and indication.

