10.10.2 Subjective Opiate Withdrawal Scale (SOWS)

Opiate withdrawal will be further assessed using the SOWS ([Handelsman, 1987](#)). The SOWS is a self-administered scale for grading opiate withdrawal symptoms. It contains 16 symptoms that the subject rates for intensity on a scale of 0 (not at all) to 4 (extremely). The SOWS will be completed by the subject according to the Schedule of Assessments (Section [1.2](#)). The SOWS may be completed in the clinic or at home depending on the requirements of the Schedule of Assessments.

Subjects will complete the SOWS at Visit 2 (De Novo Subjects only), 21, and 22/EOT (or ET Visit) in the clinic. Subjects will complete the SOWS daily between Visits 21 and 22/EOT. Subjects will complete the SOWS BID for 3 days following the last dose of study drug (from Visit 22/EOT or Early Termination) and then once daily throughout the remainder of the Safety Follow-Up Period (i.e., through Visit 24). Subjects experiencing opioid withdrawal will be treated appropriately according to the Investigator's clinical practice.

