5.0 STUDY ENDPOINTS

Key Safety Endpoint:

- Incidence, type, seriousness, and severity of adverse events (AEs) reported
- Clinical laboratory evaluations
- Electrocardiograms (ECGs)
- Vital signs (respiratory rate, pulse, heart rate, blood pressure, and temperature)
- Drug withdrawal as measured by the Clinical Opiate Withdrawal Scale (COWS) and the Subjective Opiate Withdrawal Scale (SOWS)
- Incidence of aberrant drug behavior according to MADDERS™ assessment
- Suicidality assessment (Columbia-Suicide Severity Rating Scale [C-SSRS]).

Efficacy Endpoints:

- • The mBPI-SF assessed at clinic visits.

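### Post-dose COWS and SOWS summaries mix in scores taken after a restarted opioid or withdrawal treatment, so as a measure of NKTR-181 withdrawal they may be biased downward to an unknown extent

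*SAP*

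**What the plan says.** **Endpoint and purpose.** SAP 5.0 lists among the key safety endpoints "Drug withdrawal as measured by the Clinical Opiate Withdrawal Scale (COWS) and the Subjective Opiate Withdrawal Scale (SOWS"). Protocol 6.3 gives the reason for collecting the scales after the last dose: "To capture evidence of withdrawal following discontinuation of study drug, all subjects (including ET subjects) will record SOWS measurements", with COWS assessments alongside.

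**Analysis.** SAP 8.7.2 states that "The COWS and SOWS total scores will be summarized descriptively" and that "The total score of COWS will be summarized categorically by dose level". Its one handling rule concerns incomplete forms: "If there are missing items when the total score is calculated, the total score will be set to missing". Protocol 11.9.7 adds only that item and total scores are summarised over time.

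**What subjects may take after the last dose.** Protocol 6.6.1 limits outside pain medication as follows: "Subjects must not take any medication for chronic pain during the study (through the end of the Treatment Period") unless the sponsor provided it. The same section prohibits opioids used together with NKTR-181. On withdrawal itself, Protocol 6.2 says "Subjects experiencing opioid withdrawal will be treated appropriately according to" the investigator's clinical practice, and Protocol 10.10.1 and 10.10.2 repeat this.

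**The concern.** A post-dose COWS or SOWS score reflects withdrawal from NKTR-181 only if nothing else is acting on the symptoms. A subject who has gone back to an opioid, or who is being treated for withdrawal, may score low for that reason. The planned tables would count that low score as evidence of little withdrawal.

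Treatment for withdrawal is also triggered by symptoms, so the scores most likely to be lowered this way belong to subjects who had symptoms to treat. The resulting table describes symptoms under whatever was taken afterwards. That is a different quantity from the one named in Protocol 6.3, and the SAP does not say which it intends. For a Schedule II opioid (Protocol 2.2), the withdrawal profile is a result that readers will look for.

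**Working it through.** The documents give no figure on this point to reproduce, so the check is mainly of the text.

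**1. Can the events happen in follow-up?** Yes, by two routes.
- *Opioid restart.* The ban on outside pain medication stops at the end of the Treatment Period. Protocol 6.2 moves subjects into Safety Follow-Up after Visit 22/EOT or after an ET visit. The opioid prohibition is tied to use with NKTR-181, so it does not clearly reach the time after the last dose.
- *Withdrawal treatment.* It is left to the investigator (Protocol 6.2, 10.10.1, 10.10.2). Medications to treat AEs are permitted (Protocol 6.6.2), and opioid withdrawal is a listed reason for leaving the study (Protocol 5.3), so treated cases are foreseen.

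**2. Does any section separate the affected scores?** No.

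| Place | What it does | Separates scores after an event? |
|---|---|---|
| SAP 7.1 | Subgroups by entry status and feeder treatment, if necessary | No |
| SAP 7.4, Table 1 | Assigns follow-up COWS to windows of 3 to 6 days and 7 or more days after the ET visit; has no SOWS column | No |
| SAP 8.4 | Treats concomitant medication as one category from first dose onward | No |
| SAP 8.7.1 | Counts listed withdrawal terms after the last dose as withdrawal AEs | No |
| SAP 8.7.2 | Descriptive summaries; incomplete totals set to missing | No |
| SAP 8.7.4 | MADDERS, which includes withdrawal among its event types | No |
| SAP 8.10, Protocol 11.11 | General missing-data statements | No |

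**3. How exposed is each scale?** Follow-up COWS is scheduled only at 72 hours and at 14 (± 2) days, so an event in the first three days precedes every scheduled follow-up COWS. SOWS is completed twice daily for 3 days after the last dose and then daily (Protocol 10.10.2). Some SOWS scores may therefore precede any event, but no peak or pre-event summary is planned. Early terminators receive no taper drug (Schedule of Assessments, footnote 20) and enter the same post-dose summaries.

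**4. Direction, and why no size follows.** Let q be the share of subjects with an event before the score, and d the points by which the event lowers it.

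Bias in the mean = −q × d

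Let r be the share of those q subjects who would have COWS ≥ 13 without the event, s the share of those brought below 13 by it, and b the share with COWS ≥ 13 among everyone else.

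Without the event: q·r + (1 − q)·b

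As observed: q·r·(1 − s) + (1 − q)·b

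None of q, d, r, s or b is in the documents. Purely assumed values show how wide the answer is:
- Mean: q = 5%, d = 3 gives 0.05 × 3 = 0.15 points; q = 30%, d = 10 gives 0.30 × 10 = 3.0 points.
- Share with COWS ≥ 13, b = 5%, q = 10%, r = 60%, s = 50%: 0.06 + 0.045 = 10.5% without the event, against 0.03 + 0.045 = 7.5% observed.
- With b = 5%, q from 5% to 30%, r of 30% or 60% and s of 50% or 90%, the observed share is between 88% (0.055/0.0625) and 25% (0.053/0.215) of the share without the event.

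Given that the events lower scores, the sign is the same throughout. The size is set wholly by the assumptions, and at q = 0 it is nil.

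**The case against.** The best defence is that this is an uncontrolled study with descriptive safety summaries, and symptoms observed under actual practice are a legitimate thing to describe. That stands, and it is why the all-scores summary should be kept. It does not by itself serve the purpose in Protocol 6.3, and the SAP does not say it is the target.

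The scales are also not the only evidence. Withdrawal terms after the last dose are counted as AEs, AE records include treatment of the event (Protocol 10.1.2), and MADDERS has a final-visit interview. These give a second view of withdrawal. They do not correct the scores or link them to what the subject was taking.

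Three stronger readings are tempting, and the documents do not support them.
- *That withdrawal is understated, as a fact.* That the events lower scores is pharmacological reasoning. The nearest support is indirect: Protocol 6.1.2 limits the pre-entry opioid dose to reduce withdrawal on switching. No restart or treatment rate is given, and it could be zero.
- *That a share of the roughly 250 De Novo subjects can be counted as masked.* No share is given. The 250 is an upper limit on opioid users within that group, because SAP 7.3 defines an opioid-naive De Novo group. Only subjects who would have had withdrawal can be masked. Twice-daily SOWS may also record symptoms before any restart.
- *That subjects on opioids at entry are the most prone to withdrawal.* Protocol 5.1.2 calls them non-tolerant, and by follow-up they may have had up to 52 weeks of NKTR-181. Nothing in the documents ranks the groups.

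**Conclusion.** The point holds in a limited form. SAP 8.7.2 pools post-dose COWS and SOWS scores whether or not the subject has restarted an opioid or been treated for withdrawal, and the protocol allows both. As a measure of withdrawal from NKTR-181, the summaries may be biased downward to an extent that cannot be quantified from the documents. This rests on two assumptions: that at least some subjects have such an event before a score is taken, and that the event lowers the score. COWS is the more exposed scale because it has only two scheduled follow-up assessments. The rest of the safety analysis is unaffected, and the change is worth making because it is cheap and concerns a key safety endpoint.

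**What to change.** Keep the planned all-scores summary. In SAP 8.7.2, for assessments after the last dose, use the concomitant-medication dates and indications (Protocol 6.6) to add:

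1. The number of subjects starting any opioid, and the number starting treatment for withdrawal, with timing from the last dose, by De Novo or Rollover group and by taper versus no taper (ET).
2. COWS and SOWS summaries, and peak SOWS, using only scores before the first such event. Label these as subject to informative selection, since subjects may leave the set because they are in withdrawal. State a rule for same-day events, because the protocol specifies medication dates and no times.
3. A composite withdrawal rate over all subjects entering follow-up: COWS ≥ 13 (and, separately, ≥ 5, both from the SAP's own bands) or start of treatment for opioid withdrawal. Add a sensitivity version that also counts any opioid restart as an event; otherwise an opioid restarted for pain would still hide withdrawal.

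Also reconcile Protocol 6.6, which records medications through end of study or ET, with footnote 22 of the Schedule of Assessments, which runs through study completion. Otherwise medications taken after ET may go unrecorded in the subjects who had no taper.

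The cost is SAP wording and modest extra programming. No new assessment is needed, provided medications after ET are recorded. The withdrawal rate may look less favourable.

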8.7.3 C-SSRS

The C-SSRS is a suicidality assessment instrument administered to prospectively assess the severity and frequency of suicidal ideation and behaviors. The C-SSRS identifies the full range of suicidal ideation and behavior and monitors change from visit to visit. The C-SSRS will be administered the "Baseline/Screening" version of the scale at Visit 1. It assesses suicidal ideation and behavior over the lifetime and over the past 12 months. The C-SSRS will be administered the "Since Last Visit" version of the scale at all the other required visits according to the scheduled assessments. The "Since Last Visit" version asks about any suicidal thought or behaviors the subject may have had since the last time the scale was administered.

Suicidal Ideation Score: The maximum suicidal ideation category (1-5 on the CSSRS) present at the assessment. Assign a score of 0 if no ideation is present. Suicidal ideation is a "yes" answer at any time during treatment to any one of the five suicidal ideation questions on the C-SSRS.

Suicidal behavior: A "yes" answer at any time during treatment to any one of the five suicidal behavior questions (Categories 6-10) on the C-SSRS.

Suicidal ideation or behavior: A "yes" answer at any time during treatment to any one of the ten suicidal ideation and behavior questions (Categories 1-10) on the C-SSRS.

The score at each assessment for each patient will be used for determining treatment emergence.

Treatment-emergent suicidal ideation: An increase in the maximum suicidal ideation score during treatment from baseline (excludes "lifetime" scores from the Baseline C-SSRS scale or Baseline/Screening C-SSRS scale).

Treatment-emergent serious suicidal ideation: An increase in the maximum suicidal ideation score to 4 or 5 on the C-SSRS during treatment from not having serious suicidal ideation (scores of 0-3) at baseline (excludes "lifetime" scores from the Baseline C-SSRS scale or Baseline/Screening C-SSRS scale).

Emergence of serious suicidal ideation: An increase in the maximum suicidal ideation score to 4 or 5 on the C-SSRS during treatment from no suicidal ideation (scores of 0) at baseline (excludes "lifetime" scores from the Baseline C-SSRS scale or Baseline/Screening C-SSRS scale).

An improvement in suicidal ideation at a time point is considered as a decrease in suicidal ideation score at the time point of interest (e.g., the last measurement during treatment) from the baseline measurement.

Emergence of suicidal behavior compared to all prior history: The occurrence of suicidal behavior (Categories 6-10) during treatment from not having suicidal behavior (Categories 6-10) prior to treatment.

Number of subjects with Suicidal Ideation and Suicidal Behavior during treatment will be summarized in a table. Number of subjects with suicide-related Treatment-Emergent events and shift-table of changes in C-SSRS Categories from baseline during Treatment will be summarized as well.

8.7.4 MADDERS™

Abuse-related events, also called misuse- and abuse-related events, consists of a related group of phenomena that include actual abuse (i.e., use intended to produce a euphoric effect), misuse (use outside of prescribing instructions to produce a therapeutic effect), suicide-related events, therapeutic error, overdose, diversion, addiction, withdrawal, tampering, and diversion (Smith, 2013). Until recently, these terms were used inconsistently, and consensus definitions of these terms for the purpose of clinical trials were not available, making it impossible to reliably quantify the rate of these events in studies.

Investigators are trained to identify any potentially abuse-related event, and at the time of identifying the event complete a Supplemental Adverse Event Form. In addition, a Supplemental Drug Accountability Form is completed for any subjects who have drug accountability discrepancies identified at any visit. Each time either of these events is completed, a Classification Form is completed by the investigator indicating the investigator's classification of the event in question. Finally, all subjects complete an interview-based assessment at the final visit of the study to identify any undetected abuse-related events that may have occurred during the study. Any events that have led to the completion of a Classification Form are provided to an Adjudication Committee for review and final classification.

Incidence of aberrant drug behavior according to MADDERS™ assessment will be summarized. Incidence per person-month will be summarized if applicable.

8.7.5 Clinical Laboratory Evaluations

All clinical laboratory results and change from baseline values will be summarized descriptively by treatment arm. Change from baseline via -categorical variable indicating whether the individual values are inside or outside the lab normal ranges will be tabulated using shift tables.

In addition to change from baseline summaries, hepatic function results (alanine aminotransferase [ALT], aspartate aminotransferase [AST], alkaline phosphatase [ALP], and total bilirubin [TBL]) will be summarized by treatment arm for an elevation of ALT or AST >1 to ≤ 3 X ULN; > 3 to ≤ 5 X ULN, and > 5 to ≤ 8 X ULN.

Individual results that are outside of normal range will be flagged in data listings.

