6.6.2 Permitted Medications

Subjects may use the following medications while participating in this study:

- Medications for stable diseases (e.g., metformin for diabetes. Note that NKTR-181 may increase the exposure of metformin; serum glucose levels should be monitored closely)
- Hypnotics or barbiturates if stable for at least 21 days prior to screening
- Adjuvant analgesics (e.g., antiepileptics, muscle relaxants for muscle spasms, triptans for migraine [no opioid treatment for migraine will be allowed])
- Aspirin (≤ 325 mg) for cardiovascular prophylaxis
- Antiemetics for nausea and vomiting
- Psyllium husks, stool softeners, laxatives, enemas, and peripherally acting mu-opioid receptor antagonists (PAMORAs; e.g., MOVANTIKTM) for opioid-induced constipation
- Medications to treat AEs or exacerbation of existing medical conditions
- Hormonal birth control
- Injected, topical, optical, or inhaled/nasal corticosteroids

Allowed rescue medication is described in Section [6.4](#)

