10.3 Clinical Laboratory Tests

Clinical laboratory tests will be conducted according to the Schedule of Assessments (Section 1.2). Clinical laboratory tests will be performed by a designated central laboratory. Each site will be provided instructions for specimen collection, processing, storage, packaging and shipment. Results of laboratory tests will be provided to the site.

Clinical laboratory test data will be reviewed by the Investigator or qualified sub-Investigator. Additional clinical laboratory tests may be ordered at the Investigator's or qualified sub-Investigator's discretion. All additional testing will be performed by the designated central laboratory.

The Investigator or qualified sub-Investigator will review all lab results for clinical significance. Any laboratory result deemed clinically significant will be recorded as an AE as described in Section 10.1.

Clinical laboratory tests that will be conducted for this study are listed in [Table 3](#).

Table 3: Clinical Laboratory Tests

Hematology	Chemistry	Urinalysis

 • Hemoglobin • Hematocrit • Red blood cells • White blood cells • Platelet count • Neutrophils (absolute) • Lymphocytes (absolute) • Monocytes (absolute) • Eosinophils (absolute) • Basophils (absolute) • Mean corpuscular volume • Mean corpuscular hemoglobin • Mean corpuscular hemoglobin concentration 	
 • AST • ALT • ALP • Gamma-glutamyl transferase (GGT) • Albumin • Creatinine • Glucose • Total protein • TBL • Conjugated bilirubin • Sodium • Potassium • Chloride • CO₂ content or bicarbonate • Blood urea nitrogen 	
 • Specific gravity • pH • Glucose • Protein • Bilirubin • Ketones • Leukocytes • Blood 
For positive protein, white blood cell or blood, a microscopic examination will include the following:
 
 • Red blood cells • White blood cells • Epithelial cells • Bacteria • Crystals • Casts

Abbreviations: AST; alanine aminotransferase; ALT, aspartate aminotransferase; ALP, alkaline phosphatase; CO₂, carbon dioxide; TBL, total bilirubin.

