11.9.4 Clinical Laboratory Results

All clinical laboratory results and change from baseline will be summarized descriptively. Individual results that are outside of normal range will be summarized by shift tables and flagged in data listings. Observed values and change from baseline will be summarized over time.

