8.7.6 Vital Signs and ECGs

The following variables will be derived for systolic and diastolic supine blood pressure and supine pulse rate and/or ECG parameters:

- Change from baseline.
- Treatment-emergent change from baseline, see [Appendix 1](#) (treatment-emergent decrease/increase).
- Categorical variable indicates whether the individual values are inside or outside the predefined clinical relevant ranges.
- Overall interpretation of ECGs as normal or abnormal will be recorded at the visits as specified in the assessment schedule.

Descriptive statistics will be presented for scheduled visits on observed data. In addition to the descriptive statistics, treatment-emergent abnormal value and shifts from baseline to post-baseline result will be presented. All the summaries mentioned above will be performed by the dose level in which subjects were titrated.

Data listings with flagging for values outside normal ranges will be presented.

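### The laboratory shift tables, as written in SAP 8.7.5, record only inside or outside the normal range and so cannot show the direction of a shift

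*SAP*

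**What the plan says.** SAP 8.7.5 plans four kinds of laboratory output.

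- **Continuous summaries:** "All clinical laboratory results and change from baseline values will be summarized descriptively by treatment arm".
- **Shift tables:** built on a "categorical variable indicating whether the individual values are inside or outside the lab normal ranges will be tabulated using shift tables".
- **Hepatic categories:** results "will be summarized by treatment arm for an elevation of ALT or AST", in bands defined by multiples of the upper limit of normal.
- **Listings:** "Individual results that are outside of normal range will be flagged in data listings".

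Protocol 11.9.4 gives the shift tables no direction either: "Individual results that are outside of normal range will be summarized by shift tables and flagged in data listings".

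For vital signs and ECGs, SAP 8.7.6 uses similar wording: "Categorical variable indicates whether the individual values are inside or outside the predefined clinical relevant ranges". That section, however, also cites Appendix 1 for treatment-emergent decreases and increases, and the SAP's reference tables for vital signs and ECG give lower and upper limits in separate columns. There is no counterpart for laboratory analytes.

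SAP 7.4 adds that, where several results fall in one visit window, abnormality summaries take the worst one, however far it lies from the scheduled day. It does not define worst.

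**The concern.** Clinical laboratory evaluation is among the key safety endpoints (SAP 5.0), and long-term safety is the primary objective. Many of the analytes in Protocol Table 3, such as sodium, potassium, glucose and white cells, can be abnormal on either side, and the two sides mean different things. A shift table is the usual place to see how many subjects moved, from where, and in which direction. A table that knows only inside and outside shows that subjects left the normal range but not which way. For a subject already outside the range at baseline, it cannot tell staying there from crossing to the other side.

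Glucose illustrates this. Protocol 6.6.2 permits metformin for diabetes and notes that "NKTR-181 may increase the exposure of metformin; serum glucose levels should be monitored closely". A subject whose glucose was above range at baseline and below it later would appear as unchanged.

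**Working it through.** The plan states no figure here, so the check is an enumeration followed by a comparison of passages.

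**Step 1. Collapse the full table.** With low (L), normal (N) and high (H) at baseline and after baseline there are 3 × 3 = 9 cells. With inside and outside only there are 2 × 2 = 4 cells. The nine map to the four as follows:

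| SAP cell | Full-table cells merged into it | Count |
|---|---|---|
| inside to inside | N–N | 1 |
| inside to outside | N–L, N–H | 2 |
| outside to inside | L–N, H–N | 2 |
| outside to outside | L–L, H–H, L–H, H–L | 4 |

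The counts sum to 1 + 2 + 2 + 4 = 9.

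**Step 2. Count what is lost.** The full table has 9 − 3 = 6 off-diagonal cells, each a distinct shift. Four of them (N–L, N–H, L–N, H–N) are pooled in pairs into two cells, so direction is lost. The other two (L–H, H–L) land on the diagonal beside subjects who did not move, so the shift itself disappears from the table.

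**Step 3. Which loss is likely to be larger?** The pooling of N–L with N–H needs only a normal baseline. The crossings need an abnormal baseline, and exclusion criterion 13 (Protocol 5.2) removes clinically significant laboratory abnormalities at entry. Lesser abnormalities can still be present at baseline, so crossings are possible but probably fewer. The documents give no frequencies for either.

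**Step 4. Does any other output restore the direction?**

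- *Change-from-baseline summaries* are signed and, under SAP 7.1, include the minimum and maximum. They show a large individual fall or rise, but not whether it crossed a limit or how many subjects did so, and opposite moves offset each other in the mean.
- *Listings* hold every result, but the flag is not said to distinguish low from high.
- *Adverse events* capture results judged clinically significant (Protocol 10.1.1 and 10.3), not the remainder.
- *Hepatic categories* cover ALT and AST only, and only upwards.

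Direction is therefore partly recoverable, but none of these outputs counts subjects by direction across the analytes.

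**Step 5. The worst-case rule.** Taking a laboratory shift table to be an abnormality summary, SAP 7.4 requires one worst result per window. For a two-sided analyte that choice is undefined if a window holds both a low and a high value. The schedule gives one full panel per window, and at visits outside its list of full-panel visits the protocol calls only for ALT, AST, ALP and total bilirubin. Protocol 10.3 nevertheless lets investigators order further tests, and the laboratory window for Visit 17 runs from Day 106 to Day 225. The conflict can arise, though probably not often.

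**The case against.** The strongest reply is that the wording is shorthand. The SAP never states a number of levels, and it uses much the same phrase for vital signs and ECG, where low and high limits are plainly separate. Laboratory limits would come from the central laboratory, so the lack of a limits table does not prove that the sides will be pooled. The sentence also has a stray hyphen just before the word categorical, so a qualifier may have dropped out, and table shells, which are not available here, may already settle the layout. All this is possible, but nothing in either document says it. Where the SAP wants direction it sets it out, and a programmer working from 8.7.5 alone could properly build the four-cell table.

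The second reply is that the study is descriptive and uncontrolled, and no decision rule depends on this table. That stands, and it limits the weight of the point.

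A reader might also infer three stronger things that the documents do not support:

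- *That shifts across the range are lost from the study.* They are not; Step 4 shows where they remain visible.
- *That glucose in diabetic subjects is the main problem.* The metformin note is about monitoring, not analysis. No number of diabetic or metformin-treated subjects is given, and criterion 13 limits abnormal baselines. Glucose is an illustration only.
- *That pooling doubles the background of chance abnormalities.* That needs a symmetric reference range and one side of no interest for each analyte. The documents give neither.

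**Conclusion.** The point holds for the shift tables and for the undirected worst-case rule in SAP 7.4, and no further. Read literally, the tables pool four of the six possible shifts in pairs and show the other two as no change. How many subjects this would affect cannot be stated from the documents. The conclusion assumes that SAP 8.7.5 will be programmed as worded; if the tables are already laid out as low / normal / high, only the text needs correcting. It is worth making because the output serves a key safety endpoint and the better rule is easy to state.

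**What to change.** In SAP 8.7.5, replace the inside-or-outside variable with low / normal / high for quantitative tests and normal / abnormal for qualitative urinalysis. Tabulate shifts from baseline to each visit, to the worst post-baseline low and to the worst post-baseline high, so that a subject with both kinds of result is counted in each.

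In SAP 7.4, state that for laboratory tests the worst case in a window is chosen separately for low and for high. State also that listings mark each out-of-range result L or H.

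The cost is a few sentences and slightly larger tables: nine cells in place of four per quantitative analyte and time point, plus the two worst-case tables. No new data are needed, because flagging results outside the normal range already requires the limits. Protocol 11.9.4 is compatible with the change and need not be amended.
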